### **Vital signs (office blood pressure and heart rate)**

The office blood pressure and heart rate will be measured according to the current ESH/ESC guidelines (22). A validated semi-automatic blood pressure monitor will be used to measure the blood pressure on both upper arms. The arm with the higher measured value will be used for the further measurements. In one-minute intervals the blood pressure will be recorded two more times. The first measurement will be ignored and the average of the second and third blood pressure measurement will be recorded in the CRF as office blood pressure and the average of the two heart rates will be recorded as office heart rate.

### **Hand Grip Strength**

The hand grip strength will be determined as a measure of “weakness” to calculate the “Cardiovascular Health Study Frailty Screening Scale” (23) a recommended tool to assess frailty (24). The JAMAR Hydraulic Hand Dynamometer (Model J00105) (Lafayette Instrument Company, USA) will be used, a current gold standard to measure hand grip strength (25). The recording will be done according to the Southampton protocol, a well-established protocol for measurement of grip strength in epidemiological studies of older people, which is based on the ASHT protocol (25). The patients are seated comfortably in a standard chair with legs, back support and armrests. They will rest their forearms on the arms of the chair with their wrist just over the end of the arm of the chair in a neutral position with thumb facing upwards. The handgrip dynamometer will be demonstrated to the patient. The instrument is positioned so that the thumb is round one side of the handle and the four fingers are around the other side. The handgrip dynamometer has to sit comfortably in the hand for the patient, otherwise the position will be slightly altered. The base of the hand grip instrument will have to rest on the palm of the investigator, to support the weight, but care has to be taken to not restrict the movement. The patient will be encouraged to squeeze the handgrip dynamometer as long and tightly as possible until the needle of the instruments stops rising. The result will be documented to the nearest 1kg. First the right hand strength then the left hand strength will be examined and this will be repeated twice to get six overall measurements. The highest hand grip strength recording out of all six measurements will be documented and used for the study.

### **4-meter Gait Speed test**

As a measurement of “slowness” to calculate the “Cardiovascular Health Study Frailty Screening Scale” (23) the 4 meters gait speed test will be conducted. Gait speed will be measured over a 4 meters. Subjects will begin the test from a standing position and are instructed to walk at their usual

pace a distance of 4 meters. The time will be recorded. A slow gait speed is considered with a walking speed <0.8 m/s (26, 27).

### **PWA**

The pulse wave analysis (PWA) will be performed using the SphygmoCor® (AtCor Medical, Sydney, Australia), which allows a noninvasive central blood pressure assessment. The patient will have to lie in a supine position for 15 minutes before the start of the measurements and care will be taken to assure a quite environment. Initially the brachial blood pressure will be recorded in supine position and the SphygmoCor® will be calibrated using this measurement. Using the technique of the radial applanation tonometry the pulse wave analysis will be performed with the SphygmoCor® to measure at least two PWA recordings. Only recordings with a quality index above 80% will be accepted and otherwise the measurements will have to be repeated. If there are major differences between the parameters, such as an augmentation index difference of more than 4%, a third measurement will be done. The PWA results in which the measured values are closer to each other will be used.

### **PWV**

The carotid-femoral pulse wave velocity (PWV) will be determined using the SphygmoCor® (ATCOR Medical, Sydney, Australia) immediately after performing the PWA in supine position. It is considered the noninvasive gold standard to determine the PWV and is approved by the Federal Drug Administration (FDA) (28). The recordings will be performed at the carotid artery and at the femoral artery. The distances from the palpable carotid pulse to the suprasternal notch (fossa jugularis sternalis) as well as the distances from the palpable femoral pulse to the suprasternal notch will be determined by measuring tape (29). To calculate the PWV the “Intersecting Tangents” algorithm will be chosen. The recording will be done twice. If the two results differ by more than 1,5 m/sec, a third measurement will be taken. The two PWV measurements, which are closer to each other, will be used and the other one discarded.

### **DXA-scan**

Women of child-bearing age will not perform DXA in case of a positive pregnancy test during visit 1. The participant will be transported/accompanied by the study nurse to the Outpatient Clinic of the Division of Endocrinology. DXA scan will be performed and will include scan of lumbar spine, femoral neck, distal radius and full size for the purpose of estimating percentage body fat according to the departmental Standard Operating Procedure. Body regions are defined using standard anatomical partitions. Scan areas are analysed to determine lean mass, fat mass, bone mineral content, and total body composition. If found pathologies require initiation of medical treatment according to European Guidelines for diagnosis and management of osteoporosis (18), the participant will be

informed and an appointment at the Outpatient Clinic of the Division of Endocrinology will be scheduled.

If repetition of any study procedures is not necessary, DXA-scan will be the last procedure of Visit 2.

### **Pacemaker, ICD or CRT interrogation**

Most chronic heart failure patients have, according to current guidelines, an ICD (implantable cardioverter-defibrillator) or CRT (cardiac resynchronization therapy) implanted. Those Devices can record arrhythmias and deliver therapeutic actions if necessary. Standard interrogation of the devices will be done during the study to record device parameters and recorded arrhythmic events.

## **6. Study medication**

None.

## **7. Randomization**

None.

## 9. Sample size calculation

The sample size calculation of RoC-HF is based on data from previous analyses that reported prevalence data of osteoporosis among patients with HFrEF leading to an expected prevalence of osteoporosis in RoC-HF of 20%. Osteoporosis is defined as a T-Score < -2.5 (measured by DXA), and severe osteoporosis is defined as a T-Score < -2.5 and presence of a fragility fracture, e.g., a vertebral fracture. In most of available studies on patients with HFrEF, data from DXA scans were not available. Therefore, presence of a vertebral fracture was commonly used as a criterion of osteoporosis. Thus, these studies likely underestimated the real prevalence of osteoporosis, because presence of a fracture may constitute only the "tip of the iceberg". Taken together, previous studies reported on prevalences of osteoporosis of 12 – 16% (see **Table 6**).

Table 6: Prevalence of osteoporosis as reported in previous heart failure cohorts				
Study	Patient number	Heart failure definition	LVEF in %	Data
Lyons et al (30)	623	Listed for transplant	32 +/- 16	12% with vertebral fractures
Mazziotti et al (31)	1031 (430 vs 601 healthy controls)	ICD + revision of clinical records	27 (15-45)	16.1% with vertebral fracture
Youn et al (32)	65	Acute decompensated heart failure	28 +/- 12 (males) 36 +/- 16 (females)	15% with T-Score < -2.5

Given that the RoC-HF study procedures comprise DXA scan as well as X-ray of both the thoracic and lumbar spine, we expect a prevalence of osteoporosis in RoC-HF of 20 % (95% confidence interval: 14 -26). Calculating with a significance level of 5% and a two-sided P-value leads to a number of 171

participants to be analyzed. Calculating with 20% unavailable data due to invalid ABPM, missing laboratory values or other missing parameters, we will need to enroll 205 subjects in total.

Support in sample size calculation was provided by the Institute for Medical Informatics, Statistics and Documentation of the Medical University of Graz ([name]).

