### Sample size calculation:

Based on previous epidemiological studies we expect a prevalence of osteoporosis in RoC-HF of 20 % (95% confidence interval: 14 -26). Calculating with a significance level of 5% and a two-sided P-value leads to a number of 171 participants to be analyzed. Calculating with 20% unavailable data due to invalid ABPM, missing laboratory values or other missing parameters, we will need to enroll 205 subjects in total.

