## 5. Study population

Male or female subjects with stable chronic heart failure with reduced ejection fraction.

Number of participants: 205

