5. ECG
6. Echocardiography
7. Spot urine pregnancy test for women of child-bearing age
8. 24-hours ambulatory blood pressure monitoring (ABPM).

9. Scheduling of visit 2, at least 2 days after visit 1 to facilitate performance of 24-hours ABPM. The patient will be advised to remove and switch off the ABPM device 24 hours after attaching. The patient will be advised to attend visit 2 as fasting and non-smoking over the preceding night.

## Visit 2

Visit 2 will take place at least 2 days after visit 1 to facilitate performance of 24-hours ABPM. Visit 2 will take place in the Clinical Studies Outpatient Clinic of the Department of Cardiology. The participant should be fasting and should not have smoked over the previous night. Following study procedures will be performed:

1. X-ray of the thoracic and lumbar spine. Women of child-bearing age will not perform X-ray in case of a positive pregnancy test during visit 1.
2. Re-obtainment of ABPM device. If ABPM was unsuccessful it can be repeated once, if the patient agrees.
3. Vital signs (office blood pressure and heart rate)
4. Hand Grip
5. 4m Gait Speed
6. Sampling of blood (65 mL) and spot urine (12 mL)

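### Enrolling 205 with 20% unavailable data leaves 164 analysable, not 171; the plan multiplied 171 by 1.20 where the stated loss means dividing by 0.80

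*Combined protocol and SAP*

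**What the plan says.** The sample size rests on the precision of the osteoporosis prevalence estimate, a primary aim in the synopsis. Section 9 states "we expect a prevalence of osteoporosis in RoC-HF of 20 % (95% confidence interval: 14 -26", with osteoporosis defined by a DXA T-score. The analysable number follows: "Calculating with a significance level of 5% and a two-sided P-value leads to a number of 171 participants to be analyzed". That sentence is in the sample size paragraph of section 2 and is repeated in section 9.

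The enrolment figure comes next, again in both places: "Calculating with 20% unavailable data due to invalid ABPM, missing laboratory values or other missing parameters, we will need to enroll 205 subjects". Section 5 repeats it as "Number of participants: 205", and the synopsis gives the same number.

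The 20% is a single allowance covering ABPM, laboratory and other data. The plan gives no separate rate for missing DXA and no formula for the inflation, and it does not say that the 20% is a share of the analysable number rather than of those enrolled.

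**The concern.** A 20% rate of unavailable data reads naturally as one in five of those enrolled. On that reading the required enrolment is the analysable number divided by 0.80. The plan's figure matches the analysable number multiplied by 1.20, a common slip that gives too small a number. The plan's loss rate, applied to the plan's enrolment, then does not return the plan's analysable number.

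This is the only sample size justification in the document, and it supports a primary aim. A reader who later compares achieved with planned numbers would find that 205 enrolled with 20% lost gives 164. That would look like a shortfall against 171 when it comes only from the inflation step.

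**Working it through.** **Inputs** (section 9, repeated in section 2): prevalence p = 0.20; 95% interval 14 to 26%, so half-width d = 0.06; two-sided 5% level, so z = 1.96; 171 analysable; 20% unavailable; 205 enrolled.

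**Step 1: the plan's 171.** Normal-approximation precision formula for one proportion:

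n = z² p(1 − p) / d² = 1.96² × 0.20 × 0.80 / 0.06² = 170.7, rounded up to **171**. This reproduces.

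**Step 2: the plan's 205.**

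- Adding 20% of the analysable number: 171 × 1.20 = 205.2, which rounds to **205**. This matches the plan.
- Allowing for 20% of those enrolled: 171 / 0.80 = 213.75, rounded up to **214** (check: 214 × 0.80 = 171.2). This is 9 more than the plan.

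**Step 3: what 205 delivers.**

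- With 20% lost: 205 × 0.80 = **164**, which is 7 fewer than 171 (7 / 171 = 4.1%).
- Loss that still leaves 171: 205 − 171 = 34, and 34 / 205 = **16.6%**.

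**Step 4: effect on precision.** Half-width = 1.96 × √(0.16 / n), with n rounded down. The plan gives no loss rate specific to the osteoporosis estimate, so the rates below are assumptions.

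| Assumed loss from 205 | n | Half-width (points) |
|---|---|---|
| 0% | 205 | 5.48 |
| 10% | 184 | 5.78 |
| 16.6% (34 lost) | 171 | 6.00 |
| 17.1% (35 lost) | 170 | 6.01 |
| 20% | 164 | 6.12 |
| 25% | 153 | 6.34 |
| 30% | 143 | 6.56 |

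At n = 164 the interval is 20 ± 6.12, or 13.9 to 26.1%.

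**Step 5: when the printed interval would change.** Rounding to 14 to 26% requires a half-width below 6.5 points, so n > 1.96² × 0.16 / 0.065² = 145.5. That means n of at least 146, or at most 205 − 146 = 59 lost (59 / 205 = 28.8%).

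**The case against.** **The base of the 20% is not stated.** If it is a mark-up on 171, then 205 follows by ordinary rounding and the three figures agree. That is true, but nothing in the document says so, and a share of data that will be unavailable is most naturally a share of what is collected. Even on the mark-up reading, the loss tolerated among those enrolled is 16.6%, which a reader told 20% would not know.

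**The named losses do not remove a DXA result.** Invalid ABPM or missing laboratory values alone leave the osteoporosis estimate intact, and for ABPM the Visit 2 list in section 6.c adds "If ABPM was unsuccessful it can be repeated once, if the patient agrees". This stands as a point about size: 164 is the outcome only if the full 20% falls on this estimate. It does not repair the arithmetic, because the plan itself applies the 20% to a number derived for osteoporosis prevalence. DXA can also be missing. Section 6.d says that, unless a procedure has to be repeated, "DXA-scan will be the last procedure of Visit 2", so withdrawal or loss to follow-up before then removes it, and so does a positive pregnancy test.

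**The plan sets no formal maximum half-width.** It prints whole percentages, and a difference of 0.12 points is invisible at that rounding. The point about rounding stands and keeps the severity low. The 6-point half-width is nevertheless the input that produces 171, so it is a fair yardstick for the plan's own numbers.

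**Conclusion.** The concern holds. With the 20% read as a share of those enrolled, 171 analysable, 20% unavailable and 205 enrolled are not mutually consistent. The gap is 9 participants at enrolment (214 against 205) or 7 at analysis (164 against 171).

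The severity is minor. In the case where the whole 20% falls on the osteoporosis estimate, the half-width grows by 0.12 points and the printed 14 to 26% interval is unchanged. If loss of DXA is below 16.6%, 205 gives at least the planned precision. These results assume the normal approximation, which reproduces the plan's 171, and a true prevalence of 20%. The stated figures need correcting; the size of the study does not.

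**What to change.** Keep 205 and reword the enrolment sentence in section 9 and in the sample size paragraph of section 2, in one of two ways:

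1. **As a tolerance:** enrolling 205 gives 171 analysable participants provided that no more than 34 (16.6% of those enrolled) lack evaluable data for the osteoporosis estimate. This is a limit, not an expected loss rate.
2. **Keeping 20%:** if 20% of the 205 lack evaluable data for the osteoporosis estimate, 164 are analysable and the expected 95% interval is about 13.9 to 26.1%.

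The first is the simpler choice, because it does not assign the all-purpose 20% to DXA. Holding both 20% loss and 171 analysable would instead correspond to 214 enrolled; the small gain in precision does not call for that.

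The cost is one sentence in each of two places, with no change to enrolment or procedures. As an optional clarification, separate from the error, the plan could state that the prevalence denominators are all participants with an evaluable DXA (osteoporosis) or an evaluable spine X-ray (vertebral fracture).

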## 10. Statistical analyses

Data will be illustrated by descriptive statistics using numbers and percentages for categorical variables and means and standard deviation or medians and interquartile range for continuous variables, respectively, as appropriate.

To test our primary hypotheses, the correlation between a bone formation marker or central arterial systolic pressure (independent variable, respectively) with LV systolic function (dependent variable) will be analyzed using multivariate linear regression analyses, with adjustment for age, sex, blood lipids, blood glucose, kidney function and other potentially confounding variables.

Differences of echocardiographic and other variables between patients with and without osteoporosis or other categorical variables will be compared using student's t-test, Mann-Whitney U test or analysis of variance (ANOVA), as appropriate. These differences will also be analyzed using multivariate analyses of covariance (ANCOVA), with osteoporosis (yes/no) as fixed factor, echocardiographic or other continuous variables dependent variable and age, sex, blood pressure, blood lipids, blood glucose, kidney function and other potentially confounding variables as covariates. Also other categorical variables of interest and their association with continuous outcome variables will be analyzed in the same manner.

Statistical analyses of the RoC-HF study will be the responsibility of the PIs or persons who received the permission by the PIs to perform statistical analyses. The PIs have published more than 15 original manuscripts in the field of epidemiological research, partly as first authors, and have thus proven their expertise to conduct statistical analyses. Support in statistical analyses will also be provided by [name] or PD [name] who have authored more than 100 peer-reviewed original manuscripts in the field of epidemiological research.

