### c. Exclusion criteria

1. Unplanned hospitalization within 1 month prior to the Baseline Visit.

2. Discontinuation or initiation of a pharmacologic or device treatment for HFrEF within 1 month prior to the baseline visit.
3. Coronary or peripheral revascularization procedures, valvular procedures, OR any major surgical procedure within 3 months prior to the Screening Visit.
4. Acute coronary syndrome (ACS), stroke or transient ischemic attack (TIA) within 3 months prior to the Screening Visit.
5. Any acute illness
6. Disease reducing life expectancy to < 1 year, except HFrEF
7. Recipient of any organ transplant
8. Primary significant valve disease (at least moderate to severe valve disease)

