### **Assessment of medication history**

Devices or drugs: names (INNs), dosing scheme (if applicable), date and indication of implantation/first prescription of regularly or intermittently taken drugs. Particular care will be taken to ask for treatment of:

1. Heart failure (medical): levosimendane, loop diuretics, ACE-inhibitors, angiotensin II receptor I blockers, mineralocorticoid receptor antagonists, neprilysin inhibitors, beta-blockers, ivabradine, digitalis or digoxin, amiodarone, other
2. Heart failure (devices): ICD, CRT
3. Coronary artery disease: aspirin, PY12 inhibitors, anti-anginal drugs (nitrates or similar)
4. Bone therapy: treatment for osteoporosis including PTH analogues, bisphosphonates, RANKL-antagonists, strontium-ranelate, estrogen receptor antagonists, vitamin D or analogues
5. Others: Pacemaker, oral anticoagulation, heparin, thiazide diuretics, other antihypertensive medication, drugs for psychiatric disorders

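### The T-score-only case rule counts a treated patient with known osteoporosis as a non-case once the T-score is at or above -2.5, so the planned prevalence can understate the osteoporosis burden

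*Combined protocol and SAP*

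**What the plan says.** The synopsis makes the prevalence of osteoporosis in HFrEF a primary aim. The only case rule stands in section 9: "Osteoporosis is defined as a T-Score < -2.5 (measured by DXA". The severe form adds a fracture to the same threshold ("severe osteoporosis is defined as a T-Score < -2.5 and presence of a fragility fracture"), so it is a subset and brings in no further patients. Neither rule mentions treatment or an earlier diagnosis.

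The only exclusion that concerns drug treatment is about heart failure therapy: "Discontinuation or initiation of a pharmacologic or device treatment for HFrEF within 1 month prior to the baseline visit". Patients on osteoporosis drugs can therefore enter. Assessment of medication history (section 6d) records these drugs as a separate group, "Bone therapy: treatment for osteoporosis including PTH analogues, bisphosphonates, RANKL-antagonists, strontium-ranelate" and others. The group also takes in vitamin D and its analogues. The indication is recorded with each drug.

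Section 10 uses case status in the ANCOVA ("with osteoporosis (yes/no) as fixed factor") and in the matching unadjusted tests. Separately, it regresses LV systolic function on a bone formation marker or central pressure ("the correlation between a bone formation marker or central arterial systolic pressure"), "with adjustment for age, sex, blood lipids, blood glucose, kidney function and other potentially confounding variables". Neither covariate list names bone therapy, and no section says how treated patients are classified.

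**The concern.** Effective treatment can lift a T-score back over the threshold. A rule that looks only at today's scan then removes from the numerator some patients who have the disease and are being treated for it. The Relevance section says the study is meant to measure how much osteoporosis there is in HFrEF and to have bone disease recognised as a relevant co-morbidity. Treated patients are part of that burden. The error runs in one direction, so a larger sample does not reduce it. Section 9 itself faults earlier studies for a criterion narrow enough to miss cases.

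The same patients also fall into the reference group of the osteoporosis yes/no comparisons, which can shrink those contrasts.

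A separate question arises for the bone-marker regression. If osteoporosis drugs change bone turnover, the marker in treated patients partly reflects the drug. This does not run through case status, because that model does not use it.

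**Working it through.** **1. The plan's own figure.** Inputs from section 9: expected prevalence 20%, 95% CI 14-26 (half-width 6 points), two-sided 5% level.

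n = 1.96² × 0.20 × 0.80 / 0.06² = 170.7, rounded up to 171. This matches the plan, so 6 points is the right yardstick for a shift in prevalence.

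**2. One patient traced through the plan.** Take a patient on a bisphosphonate for diagnosed osteoporosis, with a T-score now at or above -2.5. No exclusion applies. The drug and its indication are recorded. The section 9 rule classes the patient as not having osteoporosis. In section 10 the patient is in the 'no' group.

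**3. Upper bound on the shift in prevalence.** The documents give neither input, so both are assumptions: f, the share of the cohort on osteoporosis drugs (5-15%), and q, the share of those with a T-score at or above -2.5 (20-50%). The missed share is at most m = f × q.

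| f | q = 20% | q = 50% |
|---|---|---|
| 5% | 1.0 points (1.7 of 171) | 2.5 points (4.3 of 171) |
| 10% | 2.0 points (3.4 of 171) | 5.0 points (8.6 of 171) |
| 15% | 3.0 points (5.1 of 171) | 7.5 points (12.8 of 171) |

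These are upper bounds because they treat every such patient as a missed case, including anyone treated on other grounds.

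**4. Which end fits the protocol.** The Relevance section describes bone disease in HFrEF as undertreated. The largest shift needs 15% of the cohort on treatment. Counting all treated patients as cases:
- If the T-score prevalence is 20%, the total is 20 + 7.5 = 27.5%, and 15/27.5 = 55% of cases are treated.
- If 20% is the total, 15/20 = 75% are treated.

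Neither looks like undertreatment. With 5% treated, the treated share of cases is 5/22.5 = 22% to 5/20 = 25%, and the shift is 1.0 to 2.5 points.

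**5. The yes/no comparisons.** Suppose total prevalence including treated patients is 20% and missed patients resemble counted cases. The contrast then keeps 1 − m/(1 − p), where p = 0.20 − m is the T-score prevalence:
- m = 1.0 points: 1 − 0.010/0.810 = 0.988
- m = 2.5 points: 1 − 0.025/0.825 = 0.970
- m = 7.5 points: 1 − 0.075/0.875 = 0.914

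**6. The bone-marker regression.** Assume treatment shifts the marker by d = 1 to 1.5 SD.
- If LV function follows the marker level the patient would have had untreated, the slope loses v/(1 + v), with v = f(1 − f)d². For f = 0.05, d = 1: 0.0475/1.0475 = 4.5%. For f = 0.15, d = 1.5: 0.287/1.287 = 22%.
- If LV function follows the actual marker level and treatment has no other link to it, the loss is zero.
- If treated patients also differ in LV function by an assumed 0.3 SD and the marker itself has no effect, the spurious standardised slope is 0.3 × d × f(1 − f)/(1 + v), or 0.014 to 0.045 at the same two corners.

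**The case against.** **The T-score rule is a legitimate definition.** This stands. It correctly counts what it defines, and it matches the only T-score-based comparator in Table 6. A reader might infer that the planned prevalence is simply wrong. The documents do not support that: it is a valid densitometric figure that answers a narrower question than the stated aim. The rule also sits in the sample size section, and the 20% is expected partly because spine X-rays are taken as well. But no other case rule is given.

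**The models can already adjust for bone therapy.** This also stands. Both covariate lists in section 10 end with an open category that would admit it. A reader might infer that the recorded treatment data are barred from the analysis. They are not; what is missing is pre-specification. The open category does not help the prevalence or the case split, because these are classification questions.

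**The shift may be small, and some treated patients may never have met the T-score rule.** Both are fair. The X-ray section allows for treatment prompted by spine findings, so the product in step 3 is a ceiling.

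**Slope dilution is not established.** Correct. The Introduction proposes cardiovascular effects of circulating bone-derived peptides, which points towards the actual marker level. In that case drug-induced variation is real variation in exposure.

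**Conclusion.** The concern holds for the case rule. Treated patients with a T-score at or above -2.5 are counted as non-cases in a primary aim and placed in the reference group of the yes/no comparisons. Under the assumed inputs the prevalence is understated by at most 1.0 to 7.5 points, against a planned half-width of 6. The 1.0 to 2.5 points that go with 5% treated fit the protocol's own account better. Over the full range the yes/no contrast keeps about 99% to 91% of its size, if missed patients resemble counted ones. All of this depends on a treated share that the documents do not give, and if few patients are treated the effect is slight.

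For the marker regression the finding is weaker. A reader might infer that the slope is certainly diluted, but the 4.5% to 22% loss applies only if LV function follows the untreated marker level. This supports a sensitivity analysis and no more.

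**What to change.** Keep the T-score prevalence as planned. Pre-specify a second figure: T-score < -2.5, or current use of an osteoporosis-specific drug with osteoporosis as the recorded indication. Vitamin D alone should not count; this needs saying because the medication form puts it in the same group. Repeat the osteoporosis yes/no comparisons with the wider definition.

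As a secondary step, repeat the bone-marker regression without patients on osteoporosis drugs, as a sensitivity analysis.

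The cost is plan wording, one more prevalence figure, a repeat of the yes/no comparisons and one more model. All the data are already collected. The 171 does not change. If the wider prevalence is 21% to 27.5%, its half-width at 171 is 1.96 × √(0.21 × 0.79/171) = 6.1 to 1.96 × √(0.275 × 0.725/171) = 6.7 points. There is some risk of counting patients treated on other grounds, which the recorded indication limits.

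### The osteoporosis group comparisons name no unequal-variance method, although the plan expects groups of about 1 to 4

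*Combined protocol and SAP*

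**What the plan says.** Section 10 (Statistical analyses) states that differences between patients with and without osteoporosis, or between levels of other categorical variables, are to be tested by Student's "t-test, Mann-Whitney U test or analysis of variance (ANOVA), as appropriate". It continues: "These differences will also be analyzed using multivariate analyses of covariance (ANCOVA), with osteoporosis (yes/no) as fixed factor". It gives no rule for choosing among the three unadjusted tests, no check of equal variances, no Welch version and no robust standard errors.

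The group sizes follow from Section 9 (Sample size calculation): "we expect a prevalence of osteoporosis in RoC-HF of 20 % (95% confidence interval: 14 -26". On the number to be analyzed: "Calculating with a significance level of 5% and a two-sided P-value leads to a number of 171". On enrollment: "we will need to enroll 205 subjects in total".

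No section gives an SD of any outcome by osteoporosis status. The only unequal subgroup SDs in the documents are in Table 6, where one cited cohort has LVEF of "28 +/- 12 (males) 36 +/- 16 (females". Those are by sex, not by osteoporosis.

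**The concern.** Student's t-test, two-group ANOVA (the same test) and classical ANCOVA all estimate one common variance. With equal group sizes that matters little. With a 1:4 split the larger group dominates the pooled variance, while the standard error of the difference depends mostly on the smaller group. If the smaller group is the more variable, the pooled standard error is too small, p-values are too small and confidence intervals too narrow. If it is the less variable, the test is conservative and real differences are harder to detect.

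At stake is how far the p-values and intervals for the bone-status comparisons can be trusted when they are analyzed by a pooled method. These comparisons serve the protocol's stated interest in linking bone disease to cardiac function.

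**Working it through.** **1. Reproduce the plan's own figure.** With p = 0.20 and half-width d = 0.06 (from 14 to 26%):

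n = 1.96² × 0.20 × 0.80 / 0.06² = 170.7, so 171. This agrees with Section 9.

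**2. Group sizes.**
- At 20%: 0.20 × 171 = 34.2, so 34 vs 137.
- At 14%: 24 vs 147.
- At 26%: 44 vs 127.
- If all 205 enrolled were analyzed, 20% gives 41 vs 164.

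**3. Assumptions.** The SD ratio r (osteoporosis / no osteoporosis) is not in the documents and is varied from 0.5 to 2. Section 9 states the two-sided 5% level for the prevalence estimate; applying it to the group comparison is also an assumption.

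**4. Large-sample error of the pooled test under equal means.** Set the SD without osteoporosis to 1:

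- Variance the pooled test expects: Vp = [((n1−1)r² + (n2−1)) / (n1+n2−2)] × (1/n1 + 1/n2)
- True variance of the difference: Vt = r²/n1 + 1/n2
- Actual error = 2 × [1 − Φ(1.96 × √(Vp/Vt))]

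For 34 vs 137 and r = 1.5:
- Vp = [(33 × 2.25 + 136)/169] × (1/34 + 1/137) = 1.2441 × 0.03671 = 0.04567
- Vt = 2.25/34 + 1/137 = 0.07348
- √(Vp/Vt) = 0.788, and 1.96 × 0.788 = 1.545, so the error is 12.2%.

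**5. Simulation check.** Normal data, equal means, 34 vs 137; 100,000 runs per case for the pooled and Welch tests, 10,000 for Mann-Whitney:

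| r | Pooled, formula | Pooled, simulated | Mann-Whitney | Welch |
|---|---|---|---|---|
| 0.5 | 0.4% | 0.5% | 1.6% | 4.9% |
| 0.67 | 1.3% | 1.3% | 2.3% | 4.9% |
| 0.75 | 2.0% | 2.0% | 3.0% | 4.9% |
| 1 | 5.0% | 5.0% | 4.7% | 5.1% |
| 1.33 | 9.9% | 9.9% | 7.6% | 5.0% |
| 1.5 | 12.2% | 12.4% | 8.2% | 5.1% |
| 2 | 18.1% | 18.1% | 10.5% | 5.0% |

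Two further Mann-Whitney runs at r = 2 gave 10.7% and 10.9%.

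**6. Sensitivity to prevalence.** Over r = 0.5 to 2 the pooled test runs from 0.2% to 21.8% at 24 vs 147, from 0.9% to 14.8% at 44 vs 127, and from 0.4% to 18.0% at 41 vs 164. Welch stays between 4.8% and 5.3% over all group sizes tried.

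**7. ANCOVA.** With an assumed six covariates, the classical test of the osteoporosis factor gave 1.9%, 12.1% and 16.9% at r = 0.67, 1.5 and 2. With HC3 standard errors it gave 4.7%, 4.8% and 5.0%. A separate run at r = 1.5 gave 10.9% classical and 4.5% with HC3.

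**8. Price when the SDs are equal.** At 34 vs 137 and a true difference of 0.5 SD, power was 73.4% for Student's test and 72.2% for Welch.

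**The case against.** The strongest case on the other side is that the calculation is sound but says little about this study. Several stronger readings are tempting, and the documents do not support them.

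- **That the plan uses the pooled t-test.** It does not commit to that. Three tests are listed, with the choice left to the analyst, and Mann-Whitney is one of them. This objection stands. What remains is that none of the listed tests is built for unequal spread: two-group ANOVA is the pooled t-test, and Mann-Whitney is disturbed less but not immune.
- **That the error rate in this trial is between about 1% and 18%.** No SD by osteoporosis status is given, and nothing in the documents shows that the spreads differ. With equal SDs the error is 5%. That range would also join the lower end of a 1.5-fold difference to the upper end of a twofold one. For LVEF a twofold ratio is doubtful, because the inclusion criteria require a value below 50% at Visit 1 in both groups. The one subgroup ratio in the documents, 16/12 = 1.33 by sex in another cohort, would give about 2% to 10%.
- **That every bone-status comparison is affected.** Those analyzed by Mann-Whitney do not pool a variance, and outcomes with similar spread are unaffected.
- **That the linear regressions share the problem.** Their main predictors in Section 10 are a bone formation marker and central systolic pressure. Both are continuous, so the 1:4 argument does not carry over.
- **That a primary result is at risk.** The synopsis names the prevalences of osteoporosis and vertebral fractures as primary aims, and Section 10 attaches its primary hypotheses to the regressions. The group comparison is neither.

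These objections limit the size and rank of the point. They do not remove it: the imbalance is the plan's own expectation, and a better default is available at almost no cost.

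**Conclusion.** The point holds as a minor, low-cost improvement to a non-primary comparison. The group sizes come from the plan; the SD ratios are assumed. At 34 vs 137 and a nominal two-sided 5%, a pooled test would have an actual error of about 1.3% or 12% under a 1.5-fold SD difference, and about 0.5% or 18% under a twofold difference. The lower figure applies when the osteoporosis group is the less variable. If the spreads are equal there is no distortion. The figures rest on normally distributed outcomes; skewed outcomes were not examined.

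**What to change.** In Section 10, make Welch's unequal-variance t-test the default for two-group comparisons in place of Student's t-test, and Welch ANOVA the default for more than two groups in place of classical ANOVA. In the ANCOVA with osteoporosis as fixed factor, use heteroscedasticity-robust (HC3) standard errors. The regressions on continuous predictors need no change on this ground.

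The cost is one sentence and a routine software option. The statistical price is the loss of about 1 percentage point of power if the SDs turn out equal. No change to sample size or data collection is needed.
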